GeneXpert Omni (Cepheid, Sunnyvale, CA) is a point-of-care molecular diagnostic system designed for lower level health facilities. It is small (1.0 kg weight), portable, and consumes less power than previous GeneXpert systems. The standard configuration includes a single test cartridge module, a mobile device, a country-specific AC/DC power cord, a supplemental battery, and a user guide. The rechargeable battery allows for up to 4 hours of operation with voltage surge protection for unexpected power supply interruptions. Additionally, a supplemental battery can be charged for up to 12 hours of use in the event of sustained power loss. Data is stored in real-time via cloud-based connectivity to Cepheid Cloud Control using Wi-Fi or cellular networks. Training materials will be provided by Cepheid, with an anticipated training time of one half-day. Additional device-integrated videos and self-instructions are available for training reinforcement.¹⁹

Due to delays in release of GeneXpert Omni, the trial will begin with intervention sites using a modified conventional GeneXpert instrument (GeneXpert I). GeneXpert I is a one-module device with a specially-fitted dust cover that can be powered using a UPS/battery back and can be operated by a touchscreen tablet instead of a laptop computer. Sites randomized to the intervention arm will be given a solar panel charger to charge the UPS/battery pack. Once GeneXpert Omni is available, it will replace the GeneXpert I instrument. After the trial is completed, a GeneXpert Omni or GeneXpert I device will be provided to control health centers and health center staff will be trained on the use and maintenance of the device.

Of note, Xpert testing in both the control and intervention arms will occur using Xpert MTB/RIF Ultra, which is already being scaled-up in Uganda.

Process Redesign for Same-Day TB Diagnosis and Treatment

Research and Uganda NTLP staff will engage health center staff in a discussion of how to re-organize clinical, laboratory and pharmacy services to enable same-day TB diagnosis and treatment. Health center staff will be asked to identify site-specific solutions to:

1. Rapid screening for TB at registration desk and/or waiting area
2. Immediate referral of patients identified during screening as needing further testing to the lab for sputum collection
3. On-demand testing of sputum specimens and immediate reporting of results to clinicians and patients

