3.3 Interventions

Intervention arm: Health centers randomized to the intervention arm will receive the following intervention components: 1) onsite molecular testing for TB with GeneXpert as a replacement for sputum smear microscopy; 2) process redesign to facilitate same-day TB diagnosis and treatment; and 3) performance feedback of TB diagnostic evaluation quality indicators to health center staff.

Control arm: Health centers randomized to the control arm will follow the standard-of-care TB evaluation strategies, which are onsite ZN or LED fluorescence microscopy and hub-based GeneXpert testing for selected patients in accordance with Uganda NTLP guidelines.

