- **Number completing testing:** Number of eligible patients with a valid Xpert result plus number of eligible patients with a valid smear result entered into the NTLP Presumptive TB register, NTLP Laboratory register, GeneXpert laboratory requisition forms or NTLP treatment register, or with a test result recorded in the GeneXpert machine data. Testing must be completed within six months of enrolment. If the test result is missing and cannot be found in the GeneXpert machine data, it will be assumed that the patient was tested within six months of enrolment. Definitions of valid results are as follows:
 - A positive Xpert (Ultra) result with a semi-quantitative result of high, medium, low, or very low for all eligible patients; a positive Xpert Ultra result with a semi-quantitative result of trace for eligible HIV-positive patients; or a second positive Xpert Ultra result (including trace) if the initial result is trace-positive for eligible HIV-negative patients;⁶

- A negative Xpert result for all eligible patients;
- One positive OR two negative smear results for eligible HIV-negative/HIV status unknown patients.

- **Microbiologically-confirmed TB:** A positive smear and/or positive Xpert test result (as defined above) entered into the NTLP Presumptive TB register, NTLP Laboratory register, GeneXpert laboratory requisition forms, NTLP treatment register, and/or GeneXpert machine data (intervention sites only) within six months of enrolment. **Number diagnosed:** Number of eligible patients with microbiologically-confirmed TB via a positive smear and/or valid Xpert test result entered into the NTLP Presumptive TB register, NTLP Laboratory register, GeneXpert laboratory requisition form, NTLP treatment register, and/or GeneXpert machine data within six months of enrolment.
- **Number with RIF resistance detected by Xpert:** Number of eligible patients with RIF resistance identified by Xpert testing entered into the GeneXpert laboratory requisition forms and/or NTLP Laboratory registers within six months of enrolment .
- **Number with RIF resistance confirmed by culture:** Number of eligible patients with: (1) RIF resistance detected by Xpert testing entered into the GeneXpert laboratory requisition forms and/or NTLP Laboratory registers, and (2) RIF resistance confirmed by culture-based DST or a second molecular assay as determined by review of Lab Register at MDR treatment center within six months of enrolment .

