Revised detectable effect size estimates: The revised detectable effect size estimates are for the outcome being the number of patients treated for microbiologically-confirmed TB within two weeks of referral for sputum-based testing. We first used 10 months of pre-intervention period data across all 20 clinics to assess 1) the geometric mean number of patients diagnosed and treated for TB within 14 days (new primary outcome), the natural log (ln) of the geometric mean and 3) the standard deviation of the natural log at control sites, intervention sites and overall. For the pre-intervention period, the intervention clinics have a lower geometric mean number of clinic attendees who were diagnosed with TB and started on TB treatment within 14 days compared with the control arm (table 2).

Table 2: summary data from the baseline period

	Geometric mean	Mean of ln outcome	SD of ln outcome
Control	14.70	2.69	0.23

Intervention	6.49	1.87	0.32
--------------	------	------	------

We then estimated the detectable effect size (expressed as a geometric mean ratio). The calculations assume the same parameters as for the original primary outcome (10 clinics/arm, 18-month trial duration to achieve geometric mean of 268 patients/cluster in control and intervention arms). Table 3 below shows the detectable effect size assuming within-arm SD of ln outcome of 0.2 to 0.3 and power of 80-90%. The detectable effect sizes shown below are conservative (calculations do not take into account the baseline differences between arms in the new primary outcome and are based on 10-months rather than full 24-months of pre-intervention data). Final calculations will be repeated once baseline data is fully entered and available for analysis.

Table 3: Detectable effect sizes

SD of ln outcome	Geometric Mean Ratio of the new primary outcome (intervention vs control)	
	80% power	90% power
0.2	1.30	1.36
0.3	1.49	1.58

We believe a GMR of 1.30-1.58 is a reasonable detectable effect size. Xpert MTB/RIF is twice as sensitive as smear microscopy (double the number of confirmed TB cases) and we expect onsite testing to reduce pre-treatment loss to follow-up by at least half (from 30% to <15%).

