4.4.3 Primary analysis of primary outcome

Analysis will be conducted at the cluster (clinic)-level. The outcome is the count of the number treated for microbiologically-confirmed TB within two weeks of referral for sputum-based testing at the clinic-level. Initially Poisson regression will be used, with an offset at the clinic level of the total number of days the clinic contributes individuals to the study (starting from 22 October 2018). Evidence for over-dispersion will be assessed and if over-dispersion is detected then negative binomial regression will be used, using the same offset. Either model will adjust for randomisation strata and the count of microbiologically-confirmed TB cases that initiated on treatment within 14 days in the 12 month period before 22 October 2018. The exact functional form of this covariate will be identified through fractional polynomials. Further adjustment for clinic-level factors that show imbalance will be explored, though the number of adjustment factors will be limited as all are at the clinic-level. See Annex tables 4a and 4b, and 5a.

Xpert Ultra cartridges will be used in our intervention (see Outcomes Definitions Section 3.4). Two sensitivity analyses will be performed reclassifying 1) all trace-positive results as negative and 2) trace-positive results in HIV negative patients as true positive (even if not confirmed by a second positive test) to determine the impact of Ultra on the primary outcome. We expect to see trace-positive results in between 10-20% of all positive Xpert Ultra results, irrespective of study arm. Therefore, sensitivity analyses will only be done if the ratio of trace-positive results to all positive Xpert Ultra results is similar in both trial arms.

No sub-group analyses for strata defined at the individual-level (e.g., sex and HIV status) will be conducted as the primary outcome analyses are conducted at the cluster-level.

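### Both trace-positive sensitivity analyses of the primary outcome depend on trace shares being similar by arm, with no threshold or fallback, so they can be dropped when the shares differ

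*Combined protocol and SAP*

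**What the plan says.** SAP section 4.4.3 commits to two sensitivity analyses of the primary outcome, meant to show how the use of Ultra affects it. The first recodes every trace result as negative. The second counts trace results in HIV-negative patients as positive without a confirming test. The section then gives an expectation, "We expect to see trace-positive results in between 10-20% of all positive Xpert Ultra results, irrespective of study arm", and draws a condition from it: "sensitivity analyses will only be done if the ratio of trace-positive results to all positive Xpert Ultra results is similar in both trial arms". No number, interval, test or decision-maker defines similarity, and nothing is said about what happens if the condition is not met. Annex Table 5a has a row for each analysis and describes them without the condition. The SAP amendment table dates the condition to 10 January 2020 and adds no threshold.

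Related text:

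- The protocol (On-Site Molecular Testing) states that "Xpert testing in both the control and intervention arms will occur using Xpert MTB/RIF Ultra", so trace results can arise in both arms.
- SAP section 3.3 describes control care as "onsite ZN or LED fluorescence microscopy and hub-based GeneXpert testing for selected patients".
- SAP section 3.4 accepts smear or Xpert as confirmation. For a first trace result in an HIV-negative patient it requires "or a second positive Xpert Ultra result (including trace) if the initial result is trace-positive for eligible HIV-negative patients".

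**The concern.** A sensitivity analysis on trace handling is most useful when trace results may bear unequally on the two arms. The condition works the other way: a difference in trace shares is what allows both analyses to be dropped. Because similarity is undefined, the decision is also left to judgement after the data are available.

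The trigger is an imperfect guide to impact as well. Its denominator is all Ultra positives, whereas the primary outcome counts treated, confirmed cases, and control cases can be confirmed by smear. Equal trace shares therefore do not imply equal influence on the two counts. When shares are equal the analyses do run, so no check is lost in that case. The mismatch is simply a further reason not to decide on this ratio.

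These are the only planned re-estimates of the primary rate ratio under a different reading of trace. If they are dropped, Annex Table 3 still shows trace counts by arm among referred patients, but a reader could not see from the planned output what those counts do to the ratio.

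**Working it through.** **Yardstick from the plan.** SAP section 3.5 says: "We believe a GMR of 1.30-1.58 is a reasonable detectable effect size". Those limits reproduce from GMR = exp[(z0.975 + z_power) × SD × √(2/c)] with c = 10 − 1 = 9 clusters per arm (one cluster allowed for stratification) and two-sided 5% error:

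- SD 0.2: 1.302 at 80% power and 1.357 at 90% (stated 1.30 and 1.36).
- SD 0.3: 1.486 and 1.582 (stated 1.49 and 1.58).

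The figures are not in dispute; they serve only as a scale.

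**Inputs for the illustration.** From the SAP: a trace share t of 10–20% of Ultra positives. Assumed, because the documents give no figures:

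- h: chance that a trace result becomes a primary case, relative to a non-trace Ultra positive (1 or 0.5).
- fC: share of control primary cases resting on Ultra alone (1 or 0.5). All intervention cases are taken to rest on Ultra.
- d: in analysis 2, the relative rate at which unconfirmed HIV-negative trace results become added cases (0.5 or 0.25).

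**Analysis 1, trace recoded as negative.** The share of Ultra-based cases that rest on trace is a = h×t/(1 − t + h×t). With h = 1, a is 0.20 or 0.10. With h = 0.5, a is 0.10/0.90 = 0.1111 or 0.05/0.95 = 0.0526. The rate ratio is multiplied by (1 − aI)/(1 − fC×aC), where I and C denote intervention and control.

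| fC | h | Intervention 20%, control 10% | Intervention 10%, control 20% |
|---|---|---|---|
| 1 | 1 | 0.80/0.90 = 0.889 | 0.90/0.80 = 1.125 |
| 1 | 0.5 | 0.8889/0.9474 = 0.938 | 0.9474/0.8889 = 1.066 |
| 0.5 | 1 | 0.80/0.95 = 0.842 | 0.90/0.90 = 1.000 |
| 0.5 | 0.5 | 0.8889/0.9737 = 0.913 | 0.9474/0.9444 = 1.003 |

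On the plan's scale, for 20% against 10% with fC = 1:

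- 1.58 × 0.889 = 1.40 and 1.58 × 0.938 = 1.48.
- 1.30 × 0.889 = 1.16 and 1.30 × 0.938 = 1.22.

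**Equal shares.** With fC = 1 the multiplier is exactly 1. With fC = 0.5 and h = 1 it is 0.85/0.925 = 0.919 at 15% in both arms and 0.80/0.90 = 0.889 at 20% in both. The condition would let these analyses run.

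**Analysis 2, unconfirmed HIV-negative trace counted as positive.** The added fraction is g = d×t/(1 − t + h×t) and the multiplier is (1 + gI)/(1 + gC). Take fC = 1, h = 0.5 and 20% against 10%:

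- d = 0.5: 1.1111/1.0526 = 1.056; reversed shares, 0.947.
- d = 0.25: 1.0556/1.0263 = 1.029; reversed shares, 0.972.

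**Room for chance.** Suppose the true trace share is 15% in both arms. In a simple binomial simulation that ignores clustering, observed shares differ by more than 5 points in about 10% of trials with 400 and 200 Ultra positives (intervention, control), 25% with 200 and 100, and 40% with 100 and 50. These counts are assumed.

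**The case against.** The strongest defence is that the condition guards against an artefact. If semi-quantitative grades were recorded in the intervention arm but not in control, analysis 1 would remove cases from one arm only (for example 0.80/1.00 = 0.80) and the result would mislead. The confirmed-TB definition in SAP section 3.4 lists "GeneXpert machine data (intervention sites only) within six months of enrolment", which suggests unequal data sources. This risk to interpretation is real, but the SAP does not give it as the purpose. The neighbouring definition of number diagnosed lists machine data without limiting it to one arm, and the SAP amendment table allows machine data for both arms from 4 March 2020. Reporting completeness by arm deals with the risk directly, whereas dropping the analyses hides it.

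The sizes above can also be challenged, and part of that challenge stands. Taking fC = 1 sits poorly with smear-first control care, and h = 1 ignores the confirmation rule for HIV-negative patients. An HIV-negative patient whose second result is above trace would stay confirmed in analysis 1, so the model tends to overstate the shift. Where the arms rely on Ultra differently, a shift of comparable size can arise with equal shares, and there the analysis would run. In one unequal-share scenario the shift is essentially nil.

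The SAP also judges covariate imbalance without numerical thresholds, so an undefined term is in keeping with its style. There, however, the judgement governs adjustment; here it decides whether the planned checks exist at all. Trace counts in Annex Table 3, the visible empty rows in Table 5a and the protocol's promise of public data would make an omission noticeable, but none of them supplies a planned re-estimate.

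**Conclusion.** The concern holds. The current SAP text allows both planned checks of trace handling on the primary rate ratio to be cancelled when trace shares differ by arm, which runs against their stated purpose. In the unequal-share scenarios examined, the analysis 1 multiplier ranges from 0.84 to 1.125 and can be close to 1; for analysis 2 it ranges from 0.95 to 1.06. These sizes rest on assumed values of h, fC and d, and on shares at the two ends of the SAP's own range. They show that the loss could matter, not that it will.

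The primary estimate, sample size and type I error are unaffected, and unconfirmed HIV-negative trace results are already outside the primary count. The documents do not say whether trace shares by arm had been seen when the condition was added, and nothing here depends on that. The change should be made, but this is a weakness in the robustness evidence rather than in the primary analysis.

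**What to change.** In SAP section 4.4.3, delete the sentence that makes the two analyses conditional, run both, and report them in Table 5a whatever the trace shares. Add two descriptive rows by arm: the number of primary-outcome cases that rest on a trace result alone, and the completeness of semi-quantitative grades among Ultra positives. If completeness differs between arms, state that as a caveat on the reclassified ratios.

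The cost is one SAP sentence, two model runs for which Table 5a already has rows, and the two descriptive rows. No new data source is needed.

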4.4.4 Analysis of secondary outcomes

Secondary outcomes are reported as either counts, proportions, or time to event (continuous outcome), and are derived from data collected across routine data sources.

All analyses will adjust for randomisation strata. Intervention effect estimates will be reported for analyses (1) adjusting for randomisation strata only and (2) adjusting for randomisation strata and individual-level (proportions and time to event only) and clinic-level factors considered imbalanced, as outlined below. See Annex table 5b.

4.4.4.1 Count outcomes:

The analytic approach will be the same as described for the primary outcome. The outcome is the count of the respective outcome at the clinic-level. Analysis will be conducted at the cluster (clinic)-level. Either Poisson or negative binomial regression will be used, depending on over-dispersion. Adjustment will be made for the clinic-level count of the outcome using data in the 12 month period before 22 October 2018. The exact functional form of this covariate will be identified through fractional polynomials.

4.4.4.2 Proportions

The analysis will give each cluster equal weight. The overall risk for each cluster will be calculated and shown, by strata and arm. A log transformation (where necessary) will be applied to the risk for each cluster. If a cluster has no events, 0.5 event will be added to all clusters in order that the log transformation can be conducted. The mean and standard deviation of these log risks will be used to obtain the geometric mean (GM) and associated 95% CI for each arm of the study. The risk ratio is estimated using linear regression of the log risks on stratum and arm. An approximate standard error for the difference in log (GM) between arms is obtained based on the residual mean square from a two-way analysis of variance (ANOVA) of the cluster log risk on stratum, study arm and the interaction between stratum and study arm. The 95% CI is calculated from this standard error, using a t-statistic with 16 degrees of freedom. This will be the primary analysis.

Limited adjustment for individual level factors is possible; age, sex, HIV status, and ART status. Adjustment, using a complete case analysis, will only be done if data completeness for the variable is more than 80% in both trial arms and imbalance is observed (not assessed through a P-value). Logistic regression will be used to adjust for any baseline imbalance at the individual level, adopting a two-stage approach. The regression model will include terms for the adjustment factors (individual level) and strata, but not study arm. For each cluster the fitted model will be used to obtain the ratio of observed to expected (O/E) events, and a log transformation will be applied to this ratio, where appropriate.

Linear regression of the log (O/E) on stratum and arm (2-way ANOVA) will be used to estimate the risk ratio. The variance for the ratio of mean O/E is calculated from the residual mean square from an ANOVA of log(O/E) on stratum, arm and the interaction between stratum and arm. The 95% CI is calculated from this variance, using a t-statistic with 16 degrees of freedom

If imbalance is observed for the equivalent cluster-level outcome in the 12 month period before 22 October 2018, adjustment at the second stage described above will be conducted, with appropriate adjustment for the degrees of freedom for the intervention effect. The exact functional form of this cluster-level covariate will be identified through fractional polynomials.

4.4.4.1 *Time to event (continuous outcome)*

The analysis will give each cluster equal weight. The arithmetic and geometric mean for the continuous outcome of time to event (amongst all those experiencing the event) will be calculated for each cluster and shown, by strata and arm. A log transformation of the individual-level time to event will likely be necessary as the times to event may be positively skewed, resulting in geometric means. Clusters where no individuals contribute time to event outcome data will be excluded from the analysis.

ANOVA will be used to calculate either the difference in means between arms or geometric mean ratio, depending on whether a log transformation was used. This will be the primary analysis.

A two-stage approach, similar to as described above, will be used to adjust for confounders at the individual level. Limited adjustment for individual level factors is only possible; age, sex, HIV status, and ART status. Adjustment will only be done if data completeness for the variable is more than 80% in both trial arms and imbalance is observed (not assessed through a P-value). If imbalance is observed for the equivalent cluster-level outcome in the 12 month period before 22 October 2018, adjustment at the second stage described above will be conducted, with appropriate adjustment for the degrees of freedom for the intervention effect. The exact functional form of this cluster-level covariate will be identified through fractional polynomials.

4.4.5 *Sub-group analyses for secondary outcomes*

Pre-specified sub-group analyses for a subset of secondary outcomes will be conducted to assess whether the effect of the intervention differs between sub-groups. The sub-groups are (1) HIV status at enrolment (self-reported, laboratory test resulted as noted on primary data sources, or through pre-ART and ART register data extraction) defined as positive or negative, and (2) sex (male or female). The effect of the intervention will be estimated for each sub-group, and P-values for effect modification, appropriate for individual-level covariates, will be reported.¹⁰ These sub-group analyses will be conducted for the following secondary outcomes: proportion completing testing; proportion of patients referred for TB testing who are diagnosed with microbiologically-confirmed TB within 14 days; proportion of patients with microbiologically-confirmed TB who are treated within 14 days of referral for sputum-based testing; and the proportion who died within 6 months. See Annex table 5c. Results from subgroup analyses will also be summarised as forest plots.

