The minimum detectable effect size is based on published literature, our preliminary data demonstrating the increased sensitivity of Xpert Ultra vs. smear microscopy (95% vs. 40%), and reduced pre-treatment loss to follow-up expected in the intervention vs. control arms due to rapid, onsite molecular testing (7% vs. 30%). When applying these parameters to a population of 1000 individuals with TB prevalence of 10%, we would expect 95 patients to be diagnosed with TB and 88 to start treatment within 14 days in the intervention arm, and 40 patients to be diagnosed with TB and 28 to start treatment within 14 days in the control arm. Thus, the expected difference in the primary outcome proportion would be 8.8% vs. 2.8%, or 6%.⁸

Table 1. Absolute difference in the proportion of clinic attendees initiating TB treatment within 14 days of initial sputum submission, among those referred for TB testing

Average cluster size	Effect size (10 clusters per arm, $k=0.36$)		
	80% Power	85% Power	90% Power

178 (12 months)	5.9%	6.5%	7.4%
223 (15 months)	5.7%	6.3%	7.1%
268 (18 months)	5.5%	6.1%	6.9%
312 (21 months)	5.4%	6.0%	6.7%
357 (24 months)	5.3%	5.9%	6.6%

Figure 1. Effect size by cluster size. Number of clusters per arm is 10, $k=0.36$.

The primary outcome was changed to a count of the number of adults diagnosed and treated with TB at the cluster-level. The new primary outcome better reflects the intended effect of the multi-component intervention to drive more people who present to health facilities through the entire TB diagnostic evaluation cascade of care, including being screened for TB, tested for TB (if screen-positive), diagnosed with TB (if tested) and initiated on treatment (if diagnosed). Process re-design is expected to help improve the number screened and tested. Onsite molecular testing is expected to increase the numbers diagnosed (increased sensitivity) and treated (faster turn-around time and reduced workload). Performance feedback is expected to maintain improvement along each step of the cascade. Thus, the intervention is expected to increase both the number of patients entering and completing the cascade of care.

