4.4 Statistical Methods

4.4.1 General analyses principles

We will calculate and compare all effectiveness outcomes for the two trial arms using prespecified analyses following the intention-to-treat principle. Statistical analysis methods to determine intervention effect on outcomes will be used that are appropriate for CRTs with a small number of clusters. Analysis of cluster-level summaries is based on a total of 20 clusters (10 per arm), each comprised of one health center, and each being given equal weight. Effect estimates will be reported with 95% confidence intervals, and an associated P-value.

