B. Diagnosis							
Number diagnosed with microbiologically-confirmed TB (by day 1)	# GM						
Number diagnosed with microbiologically-confirmed TB (by day 14)	# GM						
Proportion diagnosed with microbiologically-confirmed TB (by day 1)	% (n/N) GM %						
Proportion diagnosed with microbiologically-confirmed TB (by day 14)	% (n/N) GM %						

Number with RIF resistance detected by Xpert/ number with RIF resistance confirmed by culture (by day 1)	# GM						
Number with RIF resistance detected by Xpert/ number with RIF resistance confirmed by culture (by day 14)	# GM						
Proportion with RIF resistance detected by Xpert/proportion with RIF resistance confirmed by culture (by day 1)	% (n/N) GM %						
Proportion with RIF resistance detected by Xpert/proportion with RIF resistance confirmed by culture (by day 14)	% (n/N) GM %						
Time to microbiologically-confirmed TB	# GM						
C. Treatment							
Number treated for TB (by day 1)	# GM						
Number treated for TB (by day 14)	# GM						
Proportion treated for TB (by day 1)	% (n/N) GM %						
Proportion treated for TB (by day 14)	% (n/N) GM %						
Number treated for microbiologically-confirmed TB (by day 1)	# GM						
Number treated for microbiologically-confirmed TB (by day 14)	# GM						
Proportion treated for microbiologically-confirmed TB (by day 1)	% (n/N) GM %						
Proportion treated for microbiologically-confirmed TB (by day 14)	% (n/N) GM %						
Proportion with microbiologically-confirmed TB treated (by day 1)	% (n/N) GM %						
Proportion with microbiologically-confirmed TB treated (by day 14)	% (n/N) GM %						
Time-to-treatment of microbiologically-confirmed TB	GM						
D. Follow-up							

Number with microbiologically-confirmed TB completing treatment	# GM						
Proportion with microbiologically-confirmed TB completing treatment	% (n/N) GM %						
Number who died within 6 months	# GM						
Proportion who died within 6 months	% (n/N) GM %						

GM geometric mean; GM % geometric mean of the cluster-level proportions

Table 5c: Sub-group analyses for selected secondary outcomes: stratum-specific unadjusted and adjusted risk ratios (95% confidence intervals) and associated P-values for interaction

Secondary outcomes	I:	C:	RR (95% CI)	P-value	Adjusted RR (95% CI)	P-value	P-value for interaction
A. Proportion completing testing							
HIV-positive	% (n/N)						
HIV-negative	% (n/N)						
Male	% (n/N)						
Female	% (n/N)						

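### Adding 0.5 event to every cluster makes the risk ratio for very sparse proportions, in practice the RIF-resistance rows, depend on clinic volume

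*Combined protocol and SAP*

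**What the plan says.** Section 4.4.4.2 of the amended SAP sets the analysis of proportions. "The analysis will give each cluster equal weight", and "A log transformation (where necessary) will be applied to the risk for each cluster". When any clinic has none, "If a cluster has no events, 0.5 event will be added to all clusters in order that the log transformation can be conducted". Then "The risk ratio is estimated using linear regression of the log risks on stratum and arm", and "The 95% CI is calculated from this standard error, using a t-statistic with 16 degrees of freedom. This will be the primary analysis". Section 4.4.1 adds: "Effect estimates will be reported with 95% confidence intervals, and an associated P-value".

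The RIF-resistance proportions go through this method. Annex Table 5b has a row labelled "Proportion with RIF resistance detected by Xpert/proportion with RIF resistance confirmed by culture (by day 1", closing bracket omitted here, and a matching row for day 14. Section 3.4 gives number enrolled as their denominator.

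Clinic volume is not expected to stay equal. Section 3.5 says that "the intervention is expected to increase both the number of patients entering and completing the cascade of care". The protocol's Table of Amendments, in its entry on symptom screening, records that referrals had risen in the intervention arm, without saying by how much. The restricted randomisation in section 4.1 includes the number of patients evaluated, but that balances pre-trial volume only.

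**The concern.** The rule adds half an event to the numerator and nothing to the denominator. In a clinic with no events the analysed value is log(0.5/N), which contains only the clinic's size. If one arm sees more patients, its mean log risk falls for that reason alone. The table would then show a ratio below 1, with an interval and P-value, for a named secondary outcome on which the arms need not differ.

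The RIF rows are the likely place for this. Section 3.4 says the control-arm process may take 7–10 days, so few control patients should have an Xpert RIF result by day 1. Confirmed resistance needs a further test read from the register of the drug-resistance treatment centre. The SAP sets no event threshold and no fallback method for such rows.

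**Working it through.** **The plan's own figures.** Two equal strata give 252 × 252 = 63,504 allocations, as section 4.1 states, so there are 5 clinics per arm per stratum. Degrees of freedom are 20 − 4 = 16, as stated; t = 2.120. Also 20 × 268 = 5360, the SAP's enrolment estimate.

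**Inputs from the documents.** Ten clinics per arm, equal weights, 0.5 added to all numerators if any clinic has zero, t on 16 df, 268 patients per clinic over 18 months (harmonic mean).

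**Assumptions.** RIF risk 0 to 0.5% of enrolled, intervention:control volume ratio 1.0 to 2.0, within-arm SD of ln(clinic size) 0.3 to 0.5, and 400 per control clinic as a second size. For scale, the protocol's 11,283 / 20 = 564 per clinic on average.

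**Exact case: no events anywhere.** Each clinic's value is ln 0.5 − ln N, so

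RR = GM(N, control) / GM(N, intervention) = 1 / (volume ratio).

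The 95% CI multiplies and divides this by exp(2.120 × s × √(2/10)), where s is the SD of ln N. With s = 0.3 the factor is exp(0.284) = 1.33:

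- volume ratio 1.25: RR 0.80 (0.60–1.06)
- volume ratio 1.5: RR 0.67 (0.50–0.89)
- volume ratio 2.0: RR 0.50 (0.38–0.66)

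With observed s = 0.2, 0.3, 0.5 or 0.7, the empty row reaches P<0.05 once the volume ratio passes 1.21, 1.33, 1.61 or 1.94. The printed geometric mean would be 0.5/268 = 0.19% where nothing occurred.

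**Simulation with equal true risk.** 20,000 trials per setting, two strata, lognormal clinic sizes, Poisson events, the SAP estimator. Ranges cover 268 and 400 per control clinic and SD 0.3 and 0.5. Each cell gives the RR, then the share of trials with P<0.05.

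| Volume ratio | No events | Risk 0.05% | Risk 0.5% |
|---|---|---|---|
| 1.0 | 1.00; 5% | 1.00; 5% | 1.00; 5% |
| 1.25 | 0.80; 15–35% | 0.82–0.85; 9–15% | 0.95–0.99; about 5% |
| 1.5 | 0.67; 40–81% | 0.71–0.74; 18–33% | 0.93–0.98; 5–6% |
| 2.0 | 0.50; 83% to over 99% | 0.57–0.61; 37–63% | 0.90–0.98; 4–6% |

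Between these risks, at volume ratio 1.5, 268 per clinic and SD 0.3, the results are RR 0.76 with 17% at 0.1%, and RR 0.82 with 8.5% at 0.2%. A risk of 0.05% is 268 × 0.0005 = 0.13 events per control clinic; 0.5% is 1.3 (268 patients) to 2.0 (400 patients).

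**A real effect.** With true risks 0.3% and 0.1% (RR 3), equal volume and 400 per clinic, the rule returns about 1.8. Power is 46%, against 44.5% for unlogged clinic risks.

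**Alternatives under equal true risk.** Unlogged clinic risks with t on 16 df reject in 0–7.5% of trials. The Poisson model with an enrolled offset rejects in 0.5–5%.

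**The case against.** Several objections have force.

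- The largest false-positive rates come from a row with no events at all. Table 5b prints n/N beside the geometric mean, so a reader would see zero against zero. This lowers the chance of being misled in that extreme case. It helps less when a handful of events is spread over both arms.
- The size depends on a RIF rate, volume ratio and spread of clinic size that the documents do not give. This stands, and is why ranges are shown.
- The log is to be taken only when needed, so unlogged risks may already be allowed. That is a fair reading, but no criterion is given, and the scale would be chosen after seeing the data.
- Only a few secondary rows are involved. The primary outcome is a count, the RIF counts use Poisson or negative binomial regression, and RIF is not a subgroup outcome. All true.
- Shrinkage of real effects costs little power. Also true; the damage is to the estimate.

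A reader might also infer that a six-month definition of confirmed resistance contradicts the day-1 and day-14 rows. It does not: the other starred diagnosis outcomes likewise have a six-month outer limit and are then assessed at the two shorter windows. What is unclear is whether the short windows apply to the Xpert detection or to its confirmation.

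**Conclusion.** The concern holds for very sparse proportions when clinic volume differs by arm. The mechanism is exact when no clinic has an event. It remains material below roughly 0.5 events per clinic and has almost gone by 1.3–2. With more patients in the intervention arm the false difference is a ratio below 1. Real effects are pulled towards 1, with little loss of power.

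It would go too far to conclude that the RIF rows will show a false difference. The documents expect and record a rise in intervention-arm patients but do not size it, and they give no RIF rate. Nor does the rule harm proportions in general: at risks of 1% and 6.7% the simulated ratio was 0.99–1.02 with rejection of about 4–5% (268 per control clinic). The trial's main conclusion does not depend on these rows. The point still merits correction, because the rule as written would print misleading inference in rows that the plan asks for.

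**What to change.** In section 4.4.4.2, replace the 0.5 rule for proportions with zero-event clinics by one of two methods, named in advance:

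1. unlogged clinic risks, giving a risk difference with t on 16 df; or
2. the clinic-level Poisson or negative binomial model already planned for counts, with log(number enrolled) as offset.

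Add that when an arm has no events, or the total is below a pre-set count, the row shows n/N only, with no ratio or P-value. This is needed because the count model gives no usable ratio when an arm is empty. At 0.05% risk and volume ratio 1.5 that happens in about 15% of trials with 400 patients per control clinic and about 33% with 268.

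For confirmed RIF resistance, state whether the day-1 and day-14 windows apply to the Xpert detection or to the confirmation. If to the confirmation, compare arms only over the six-month window.

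The change is to SAP wording and needs no new data. The cost is that these few rows lose uniformity with the other proportions, and some will carry no ratio.
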